5.6.8 Laboratory

Laboratory data are evaluated in standard international units as provided by the central laboratory. The following tests are considered:

- Hematology: hemoglobin, hematocrit, erythrocyte count, leukocyte count with differential counts, platelet count.
- Chemistry: aminotransferases (aspartate aminotransferase [AST] / alanine aminotransferase [ALT]), alkaline phosphatase [AP], total and direct bilirubin, lactate dehydrogenase, creatinine, creatinine clearance, uric acid, glucose, sodium, potassium, total protein, albumin, thyroid hormones (triiodothyronine [free T3], thyroxine [free T4]) and thyroid-stimulating hormone.
- Urinalysis: Urine albumin-to-creatinine ratio (UACR).

For woman of childbearing potential, urine as well as serum pregnancy tests are performed, but these results will not be summarized as part of the laboratory data. Positive pregnancy tests (if any) will be reported.

Results of local laboratory tests (collected on the **Local Laboratory** eCRF) may be used to identify marked abnormalities, but only if no central laboratory test has been performed in the same time window. Local laboratory test results will not be used in summaries, but will still be listed.

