7.3.5 Laboratory assessments

7.3.5.1 Type of laboratory

A central laboratory (see central laboratory manual for contact details) will be used for all protocol-mandated laboratory tests (except PK), including re-tests due to laboratory abnormalities and laboratory tests performed at unscheduled visits. Central laboratory data will be automatically transferred from the central laboratory database to Actelion's clinical database. In exceptional cases (e.g., subject is hospitalized in a different hospital from the study center due to a medical emergency, or missing central laboratory values)

Essential hypertension Protocol AC-080A201 Version 3 30 May 2016, page 61/112

Confidential

local* laboratory results (with the corresponding normal ranges) will be entered into the clinical database via dedicated eCRF pages.

If a central laboratory sample is lost or cannot be analyzed for whatever reason, the investigator will collect an additional sample as soon as possible for repeat analysis, unless a local laboratory sample was collected within the same time-window and these test results are available.

Central laboratory reports will be sent to the investigator. In the event of specific (pre-defined) laboratory abnormalities, the central laboratory will alert Actelion and the concerned site. Alert flags that will trigger such notifications are displayed in Appendix 2.

All laboratory reports must be signed and dated by the investigator or delegate within 5 working days of receipt and filed with the source documentation. The investigator/delegate must indicate on the laboratory report whether abnormal values are considered clinically relevant or not. Clinically relevant laboratory findings that are known at the time of signature of informed consent must be recorded on the medical history page of the eCRF. Any clinically relevant laboratory abnormalities detected after signature of informed consent must be reported as an AE or SAE as appropriate [see Section 10], and must be followed until the value returns to within the normal range or is stable, or until the change is no longer clinically relevant. Further laboratory analyses should be performed as indicated and according to the judgment of the investigator.

At Screening (Visit 1) historical laboratory data can be used to check exclusion criterion 15 [see Section 4.4], if not older than 3 months. If not available, a blood sample must be taken for analysis by central laboratory.

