7.3.5.2 Laboratory tests

The total amount of blood collected during the study is provided in the laboratory manual. This is approximately 96 mL (10 mL for hematology / clinical chemistry including pregnancy test [if applicable], 8 mL for PK and pharmacodynamic [PD] samples, and 2 mL for pregnancy test at follow-up visit):

- At Visit 1: One sample, only if no historical (within 3 months to this visit) laboratory data available;
- At Visits 3 and 4: One sample;

^{*} Except historical local laboratory data of Visit 1.

Essential hypertension Protocol AC-080A201 Version 3 30 May 2016, page 62/112

Confidential

• At Visits 5, 6, and 7: Two samples; one for the hematology / clinical chemistry / pregnancy analysis, and one for PK and PD analysis); and

- At Visit 8: One sample.
- Follow-up visit, only for women of childbearing potential: One sample for serum pregnancy test.

Hematology

- Hemoglobin, hematocrit
- Erythrocyte count
- · Leukocyte count with differential counts
- Platelet count.

Clinical chemistry

- Aminotransferases (AST/ALT), alkaline phosphatase, total and direct bilirubin, LDH
- Creatinine, creatinine clearance
- Uric acid
- Glucose
- Sodium, potassium
- Protein, albumin
- Free T3, free T4, thyroid stimulating hormone (TSH).

Urinalysis

At Visits 4, 5, 6, 7 and 8 a midstream, clean-catch urine specimen (about 10 mL) will be collected for dipstick analysis and determination of UACR.

UACR determination:

The collected urine will be transferred into a standard urine collection tube for shipment to central laboratory. Details about the collection, sampling, storage, shipment procedures, transfer and reporting of results can be found in the laboratory manual.

Dipstick analysis:

- Bilirubin, urobilinogen
- Blood
- Glucose
- Ketone
- Leukocytes
- Nitrite

Essential hypertension Protocol AC-080A201 Version 3 30 May 2016, page 63/112

Confidential

- pH
- Protein.

Urine dipsticks provided by the central laboratory will be used to perform the urinalysis. The test should be performed and analyzed at the site. The results must be documented in the source documents / subject charts. No data will be collected in the eCRF. Clinically relevant findings meeting the definition of an AE (new AE, or worsening of previously existing condition) [see Section 10.1] will be recorded accordingly on the AE page of the eCRF.

Pregnancy test

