11.3.5.2 Laboratory parameters

Descriptive summary statistics by visit and treatment group will be provided for observed values and absolute changes from baseline, in both hematology and blood chemistry and urine (only UACR) laboratory tests. In order to minimize missing data and to allow for unscheduled visits, all recorded assessments will be assigned to the most appropriate visit timepoint according to the best fitting time-window for that assessment.

Actelion internal guidelines will be used for the definitions of marked abnormalities and for the standardization of numeric values obtained from different laboratories and/or using different normal ranges. Standard numeric laboratory variables are transformed to standard units. All laboratory data transferred are taken into account regardless of whether they correspond to scheduled (per protocol) or unscheduled assessments.

Marked laboratory abnormalities will be summarized for each laboratory parameter by treatment group providing their incidence and frequency. Absolute values and changes from baseline of laboratory parameter values during the course of the study will be summarized using the usual location and scale summary statistics by treatment group.

Laboratory parameters include:

- Hematology: hemoglobin, hematocrit, erythrocyte count, leukocyte count with differential counts, platelet count.
- Blood chemistry: AST, ALT, alkaline phosphatase, total and direct bilirubin, LDH, creatinine, creatinine clearance, uric acid, glucose, sodium, potassium, protein, albumin, free T3, free T4, TSH.
- Urine: UACR.

The number and percentage of subjects with treatment-emergent laboratory abnormalities will be tabulated by treatment group.

Essential hypertension Protocol AC-080A201 Version 3 30 May 2016, page 90/112

Confidential

11.3.5.3 12-lead ECG

Descriptive statistics by visit and treatment group will be provided for observed values and absolute changes from baseline, in numeric 12-lead ECG values (PR, QRS, QT, QTcB and QTcF). In order to minimize missing data and to allow for unscheduled visits, all recorded assessments will be assigned to the most appropriate visit time point according to the best fitting time-window for that assessment.

In addition, treatment-emergent morphological ECG abnormalities will be summarized.

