Baseline for laboratory data is defined in Section 5. Each condition is triggered at any post-baseline time point of measurement up to the double-blind treatment end date plus 30 days (included). When determining double-blind treatment-emergent marked laboratory abnormalities, all assessments (including the unscheduled ones) are considered.

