11 GENERAL DEFINITIONS AND DERIVATIONS

11.1 Time windows

To allow analysis of data at the relevant planned (scheduled) visits, all recorded assessments, including unscheduled ones, are re-assigned to the most appropriate visit according to the best fitting time window for that visit [see Table 5]. Note that there are no 'gaps' between the visit windows in order to keep all values in the analysis.

Table 5 Visit time windows

Visit	Target day*	Min. day	Max. day
1	-42	-	-35
2	-28	-34	-18
3	-7	-17	-4
4	1	-3	1
5	14	1	21
6	28	22	42
7 - I	55	43	EOT***
7 - II**	56	EOT + 01 m	EOT + 25 h
8	70	EOT + 25 h 01 m	No limit

* Number of days from start of double-blind treatment.

** Only for ABPM.

*** For OBPM use EOT + 05 m (for the time of the average SiDBP)

ABPM = ambulatory blood pressure monitoring; EOT = End-of-Treatment; OBPM = office blood pressure measurement; SiDBP = sitting diastolic blood pressure.

For assessments for which time is collected, please use the following rules:

- Target day = Target day and time 12:00
- Min. day = Min. day and time 0:00
- Max. day = Max. day and time 23:59

Visit 4 / Day 1

- Target day 1 = Start date/time of DB treatment
- Max. day1 = Start date/time of DB treatment

Visit 5 / Day 1

- Min. day 1 = Start date/time of DB treatment + 1 minute

Visit 7 - I / EOT

- Max. day = End date/time of DB treatment

Visit 7 - II / EOT

- Min. day = End date/time of DB treatment + 1 minute

In the event that there is more than one value within the same time window, the value closest to the planned assessment date will be taken. In the event of equidistant values from the planned time point, the last assessment will be considered for the analyses. Where multiple assessments fall on the same day the latest is then used.

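### A routine central laboratory draw can block a local emergency value from the by-arm marked-abnormality tables (SAP 5.6.8)

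*SAP*

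**What the plan says.** Protocol 7.3.5.1 sends protocol-mandated tests other than PK to the central laboratory, including re-tests and unscheduled-visit tests. Local results, with their normal ranges, go onto dedicated eCRF pages in exceptional cases. The two examples given are that the "subject is hospitalized in a different hospital from the study center due to a medical emergency", or that central values are missing.

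SAP 5.6.8 limits what is done with them. Local results "may be used to identify marked abnormalities, but only if no central laboratory test has been performed in the same time window". It adds: "Local laboratory test results will not be used in summaries, but will still be listed". I take summaries here to mean the by-visit descriptive tables. If the word also covered the marked-abnormality tables, the restriction would be wider still.

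The windows are those of SAP Table 5 (Section 11.1), under which "all recorded assessments, including unscheduled ones, are re-assigned to the most appropriate visit according to the best fitting time window".

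Other sections are broader:

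- SAP 5.6.8.1: "When determining double-blind treatment-emergent marked laboratory abnormalities, all assessments (including the unscheduled ones) are considered". A condition is met at any post-baseline time up to 30 days after the end of double-blind treatment (EOT).
- SAP 10.9.4.1 includes unscheduled values and divides by all subjects with any post-baseline laboratory measurement.
- Protocol 11.3.5.2: "All laboratory data transferred are taken into account regardless of whether they correspond to scheduled (per protocol) or unscheduled assessments". It also plans to standardize values from different laboratories.

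SAP 4.1, which lists changes from the protocol's analyses, does not mention the restriction.

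**The concern.** Keeping one value per window suits by-visit means. A marked abnormality is an ever/never count. Under SAP 5.6.8.1 two central values in one window both count, but a local value beside a central one does not. The local value may come from an acute event. The central value that displaces it may be a routine sample up to 14 days away at the nominal schedule (Day 28 against Day 42).

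Treatment-emergent marked laboratory abnormalities are a named safety endpoint (protocol 6.2), and the trial is meant to choose Phase 3 doses on the balance of efficacy and tolerability (protocol 1.3). Protocol 1.2.1 reports treatment-related hemoglobin decreases and one AST/ALT rise at 100 mg, so these parameters matter. A blocked subject is not treated as missing. He or she stays in the denominator as a subject without the abnormality.

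**Working it through.** **1. Draw schedule.** Protocol 7.3.5.2 states: "At Visits 5, 6, and 7: Two samples; one for the hematology / clinical chemistry / pregnancy analysis". It lists one sample each at Visits 1, 3, 4 and 8. Check against the stated volume: 7 draws × 10 mL (Visits 1, 3, 4, 5, 6, 7, 8) + 3 × 8 mL (PK/PD) + 2 mL (follow-up pregnancy test) = 96 mL, which is the protocol's figure.

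**2. Draws against windows (SAP Table 5).**

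| Window | Days | Scheduled central draw |
|---|---|---|
| Visit 5 | 1 to 21 (21 days) | Day 14 ± 3 |
| Visit 6 | 22 to 42 (21 days) | Day 28 ± 3 |
| Visit 7-I | 43 to EOT (13 days if EOT is Day 55) | Day 55 ± 5 |
| Visit 8 | EOT + 25 h 01 m, no upper limit | Day 70 ± 3 |

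Visit 7-II is for ABPM only. All 4 of the 4 post-baseline laboratory windows hold a scheduled central draw.

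**3. Subject who continues and attends every visit.** 21 + 21 + 13 = 55 days. A local value is blocked on 55 of 55. The Visit 8 draw likewise blocks local values from EOT + 25 h 01 m to EOT + 30 days. If a fraction m of central draws is missing, the blocked share is 1 − m. The documents give no m; assuming 2% to 20%, the blocked share is 98% to 80% (95% at m = 5%).

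**4. Subject who stops treatment on the day of the emergency, day d.** The main SAP does not say where the premature-EOT draw (Visit 9, within 7 days of the last dose) is mapped, so I take both readings.

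- *Draws after EOT go to Visit 8.* The local value is kept if d falls before the window's scheduled draw: 13 days (1 to 13) + 6 (22 to 27) + 12 (43 to 54) = 31 of 55, or 56%. Moving the Visit 5 and 6 draws by 3 days gives 10 + 3 + 12 = 25 (45%) or 16 + 9 + 12 = 37 (67%).
- *The Visit 9 draw falls in the Visit 5 or 6 day range.* It then blocks those windows too: 0 + 0 + 12 = 12 of 55, or 22%.

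**5. Mixture.** Let p be the share of emergencies that stop treatment and k the share kept among them. With no missed draws, blocked = (1 − p) + p(1 − k). The documents give no p; I assume 25% to 50%, with every day equally likely.

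- k = 31/55: 0.75 + 0.25 × 0.436 = 86%; 0.50 + 0.50 × 0.436 = 72%.
- k = 12/55: 0.75 + 0.25 × 0.782 = 95%; 0.50 + 0.50 × 0.782 = 89%.

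These are shares of local values kept out by the rule. They are not shares of events lost, because central re-tests and AE reporting also capture events.

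**6. Which values go.** Two illustrations:

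- *Potassium.* The central value is normal on Day 28. A hospital value above 6.0 mmol/L on Day 36 is corrected before the next visit. Protocol 5.1.12 and the Appendix 2 repeat alerts set no potassium re-test. The table shows no case.
- *ALT.* The hospital value is 10 × ULN on Day 36, and a central re-test in the same window lies between 5 and 8 × ULN. The table shows HHH. The HHHH grade (above 8 × ULN) is lost.

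**7. Weight of one case.** SAP 4.2 gives 490 randomized. 490/6 ≈ 82 per arm, so one reclassified subject moves an arm's percentage by about 1/82 = 1.2 points.

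**The case against.** **Central follow-up catches sustained events.** Protocol 5.1.12 requires an aminotransferase re-test within 48 h at 3 to 8 × ULN, weekly liver monitoring after discontinuation, and a hemoglobin re-test within 10 days after a fall of more than 20 g/L. Section 8.4 adds the Visit 9 laboratory test, and 7.3.5.1 asks that any clinically relevant abnormality be followed. Re-tests go to the central laboratory, and SAP 5.6.8.1 counts unscheduled values. This stands. It leaves exposed the values that have normalized or been corrected by then, such as potassium, creatinine, hemoglobin after transfusion, or a peak grade.

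**Events appear elsewhere.** A reader might infer that severe cases would be visible only in a listing. The documents do not support that. Clinically relevant abnormalities must be reported as AEs or SAEs, inpatient hospitalization is an SAE criterion, and AEs, SAEs and AEs leading to discontinuation are tabulated by arm. An independent liver board reviews hepatic events, and local values are listed with marked abnormalities flagged (SAP 10.9.4). These routes rest on investigator judgment and preferred terms, however, and do not reproduce the LL to HHHH thresholds.

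**Local values are not always lost.** A reader might also infer that local values almost never count. That holds only for subjects on schedule. Missing central values are one of the protocol's two reasons for collecting local data, and the rule keeps those results.

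**The conflict is ambiguous.** The reference in SAP 5.6.8.1 to all assessments may contrast scheduled with unscheduled, not central with local. In protocol 11.3.5.2 the data transferred may mean central data only, since 7.3.5.1 speaks of local results as entered. The passages are poorly aligned, but calling them a plain contradiction goes too far.

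**Central priority is a legitimate choice.** A single assay avoids between-laboratory noise. But the SAP already accepts local values for this purpose when no central test exists, so comparability cannot be the full reason to refuse them otherwise.

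**Conclusion.** The point holds in limited form. For a subject who stays on schedule, the rule blocks a local value throughout the double-blind period. For a subject who stops on the day of the emergency, it blocks between 18 of 55 days (draws after EOT mapped to Visit 8, with Visit 5 and 6 draws 3 days late) and 43 of 55 (Visit 9 draw counted in the Visit 5 or 6 window). The effect is confined to the by-arm marked-abnormality tables and falls mainly on transient or quickly corrected values and peak grades, whose subjects are then counted as non-cases.

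The day counts assume EOT on Day 55 and an emergency equally likely on any day. The documents do not say how often local results arise, beyond calling them exceptional, so the number of subjects affected cannot be estimated. Severity is minor to moderate.

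**What to change.** Reconcile SAP 5.6.8, SAP 5.6.8.1 and protocol 11.3.5.2 by amending SAP 5.6.8 along these lines:

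- Every local result with a date and a reference range counts toward treatment-emergent marked abnormalities from the start of double-blind treatment to EOT + 30 days, whether or not a central test falls in the same window.
- Where the threshold is a multiple of ULN, the local ULN is used.
- Local results stay out of the by-visit summaries.
- Subjects whose abnormality comes from a local laboratory only are footnoted.

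Record the rule in SAP 4.1 or 5.6.8 so that its relation to the protocol is explicit. The amended rule makes this table independent of window mapping. The SAP should still state where Visit 9 draws, and laboratory values between EOT and EOT + 25 h, are placed for the by-visit tables.

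The cost is a short SAP edit and a small programming change, since the results and normal ranges are already collected on the eCRF. The downside is some between-laboratory variation, including for creatinine thresholds set against a central baseline. The footnote discloses it.

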5.6.8.1 Treatment-emergent marked laboratory abnormalities

The marked laboratory abnormalities are given in [Table 2](#), copied from appendix 1 of the protocol.

Table 2 **Thresholds for marked laboratory abnormalities**

Parameter	LL	LLL	HH	HHH	HHHH
Hematology					
Hemoglobin	< 100 g/L (< 10 g/dL; < 6.2 mmol/L)	< 80 (< 8 g/dL; < 4.9 mmol/L;)	Increase in > 20 g/L above ULN or above baseline if baseline is above ULN	Increase in > 40 g/L above ULN or above baseline if baseline is above ULN	
Hematocrit	< 28% for females < 32% for males	< 20%	> 60% in men > 55% in women	> 65%	
Leukocytes	< $3.0 \times 10^9/L$ (< 3000/mm ³)	< $2.0 \times 10^9/L$ (< 2000/mm ³)	> $20.0 \times 10^9/L$ (> 20,000/mm ³)	> $100.0 \times 10^9/L$ (> 100,000/mm ³)	
Platelet count	< $75 \times 10^9/L$ (< 75,000/mm ³)	< $50 \times 10^9/L$ (< 50,000/mm ³)	> $600 \times 10^9/L$	> $999 \times 10^9/L$	
Neutrophils	< $1.5 \times 10^9/L$ (< 1500/mm ³)	< $1.0 \times 10^9/L$ (< 1000/mm ³)	NA	NA	
Eosinophils	NA	NA	> 5.0×10^9 or > 5% (> 5000 cells/mm ³)	NA	
Lymphocytes	< $0.8 \times 10^9/L$ (< 800/mm ³)	< $0.5 \times 10^9/L$ (< 500/mm ³)	> $4.0 \times 10^9/L$ (> 4000/mm ³)	> $20 \times 10^9/L$ (> 20,000/mm ³)	

Parameter	LL	LLL	HH	HHH	HHHH
Blood Chemistry					
AST (U/L)	NA	NA	> 3 × ULN	> 5 × ULN	> 8 × ULN
ALT (U/L)	NA	NA	> 3 × ULN	> 5 × ULN	> 8 × ULN
AP	NA	NA	> 2.5 × ULN	> 5 × ULN	
Bilirubin Total (µmol/L)	NA	NA	> 2 × ULN	> 5 × ULN	
Creatinine	NA	NA	> 1.5 × ULN or > 1.5 × baseline	> 3 × ULN or > 3 × baseline	
Creatinine clearance	< 60 mL/min	< 30 mL/min	NA	NA	
Glucose	< 3.0 mmol /L (< 55 mg/dL)	< 2.2 mmol /L (< 40 mg/ dL)	> 8.9 mmol /L (> 160 mg/dL)	> 13.9 mmol /L (> 250 mg/ dL)	
Sodium		< 130 mmol/L (< 130 mEq/L)	> 150 mmol/L (> 150 mEq/L)	> 155 mmol/L (> 155 mEq/L)	
Potassium	< 3.2(mmol/L)	< 3.0(mmol/L)	> 5.5(mmol/L)	> 6.0(mmol/L)	
Uric acid	NA	NA	> 590 (umol/L) (> 10 mg/dL)	> 720 (umol/L) (> 12 mg/dL)	
Albumin	< 30 g/L (< 3.0 g/dL)	< 20(g/L (< 2.0 g/dL)	-	-	

ALT = alanine aminotransferase; AP = alkaline phosphatase; AST = aspartate aminotransferase; NA = not applicable; ULN = upper limit of normal.

Treatment-emergent marked laboratory abnormalities are those marked abnormalities with onset date after the double-blind treatment start date [see definition in Section 11.2] and before or on double-blind treatment end date [see definition in Section 11.4] plus 30 days (included), that were not present at baseline.

Baseline for laboratory data is defined in Section 5. Each condition is triggered at any post-baseline time point of measurement up to the double-blind treatment end date plus 30 days (included). When determining double-blind treatment-emergent marked laboratory abnormalities, all assessments (including the unscheduled ones) are considered.

5.6.9 Other safety variables

Not applicable.

5.7 Quality of life variables

Not applicable.

5.8 Pharmacoeconomic variables

Not applicable.

5.9 Pharmacodynamic variables

Trough plasma concentrations of ET-1, measured at steady state at Weeks 2, 4 and 8 in DB treatment period (Period II). Trough is defined as a sample taken in the morning of the visit prior to study treatment administration of that visit.

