5.1.10 Study treatment dose adjustments and interruptions

Study treatment dose adjustments are not permitted.

Study treatment may be temporarily interrupted in response to an AE, a diagnostic or therapeutic procedure, a laboratory abnormality, or for administrative reasons. Study-specific criteria for interruption of study treatment are described in Section 5.1.12.

^{*} From both bottles

Essential hypertension Protocol AC-080A201 Version 3 30 May 2016, page 49/112

Confidential

If study treatment intake is interrupted by the subject for any reason, she/he must immediately inform the investigator.

Interruptions of study treatment should be kept as short as possible. If treatment is stopped for more than 4 consecutive days, re-introduction is not permitted and treatment must be permanently discontinued [see Section 5.1.12].

Study treatment interruptions must be recorded in the eCRF.

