6 STUDY ENDPOINTS

6.1 Efficacy endpoints

6.1.1 Primary efficacy endpoint(s)

The primary efficacy endpoint is the change from baseline to Week 8 of DB treatment period (Period II) in mean trough (i.e., 24 h post-dose) SiDBP, measured by OBPM.

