7.4.1 Blood sampling

Blood samples will be drawn at trough (before morning dose) at Week 2 (Visit 5), Week 4 (Visit 6) and Week 8 (Visit 7) [See Table 1]. Blood sampling will take approximately 1 minute. Procedures for sampling for PK and PD measurements are as follows: blood (4 mL for ACT-132577 measurements) will be collected by direct venipuncture or via an i.v. catheter placed in an antecubital vein in the arm in Vacutainer® or equivalent tubes containing K3-EDTA. Immediately following collection of the required blood volume, the Vacutainer® will be slowly tilted backwards and forwards (no shaking) to bring the anti-coagulant into solution, and immediately cooled in an ice water bath. Within 30 minutes of collection, the Vacutainer® will be centrifuged at approximately 1500 g for 10 minutes at 4 °C. The plasma for PK (approximately 1.5 mL) will be transferred into one labeled polypropylene tube to avoid carryover of erythrocytes. The PD plasma sample (about 500 μL) will be

^{*} If blood must be taken for hematology / clinical chemistry laboratory analysis, a serum pregnancy test must be performed.

Essential hypertension Protocol AC-080A201 Version 3 30 May 2016, page 64/112

Confidential

transferred into 1 labeled polypropylene tube. All samples will be stored in an upright position at -80 ± 20 °C. The date and exact actual clock time of collection of each blood sample will be entered in the eCRF as well as the exact dates and time of the drug administration prior and after blood draw.

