2.2 Study visit and assessment schedule

[Table 1](#) shows a schematic representation of the assessments during the study.

*Electronically transferred to sponsor.

** Visit 1 (Screening) can last up to 72 h for obtaining informed consent and performing required assessments.

1. Height is only measured at Visit 1.
2. Serum pregnancy test only for women of childbearing potential. Result is transferred electronically to sponsor.
3. All AEs and SAEs that occur after signing the Informed Consent Form and up to 30 days after last DB study treatment intake must be reported.
4. Historical ECG is accepted if not older than 6 months.
5. Historical blood laboratory data is accepted to check exclusion criterion 15, if not older than 3 months. In such a case, for women of childbearing potential a urine pregnancy test must be performed. If no historical report is available, a blood sample to be taken for laboratory analysis (including pregnancy test for women of childbearing potential) by central laboratory.
6. Run-in period is 4 weeks before randomization for anti-hypertensive treatment naïve subjects. Visit 1 is combined with Visit 2. Run-in period is 6 weeks before randomization for subjects on anti-hypertensive treatment. Visit 1 and Visit 2 must be performed.
7. Only urine pregnancy test for women of childbearing potential. Result is captured in the eCRF.
8. Only for subjects who were on anti-hypertensive drugs at Visit 1 (i.e., had to perform a Visit 2).
9. If subject discontinued study treatment during run-in period (i.e., between run-in visits) or at an in-person run-in visit (e.g., Visit 3), these tests may not be performed
10. Unscheduled visits may be performed at any time during the study and may include all or some of the indicated assessments, based on the judgment of the investigator.
11. For women of childbearing potential a visit must be organized instead of the telephone call to perform the serum pregnancy test at the site. However, if a woman of childbearing potential discontinued study treatment during the run-in period, a telephone call can be made instead of the visit.
12. Upon investigator's judgment, a home monitoring device will be dispensed to monitor BP at home, if necessary.
13. Sample to be taken at trough (i.e., prior to study treatment intake).

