5.5.1 Primary efficacy endpoint(s)

The primary efficacy endpoint is the change from baseline to Week 8 of DB treatment period (Period II) in mean trough (i.e., 24 hours post-dose) SiDBP, measured by OBPM.

Baseline is defined as described in Section 5. Week 8 is the time window of Visit 7 [Section 11.1].

SiDBP is retrieved from the SDTM VS domain selecting VSTESTCD="DIABP" and VSSCAT='Average'.

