6 DEFINITION OF PROTOCOL DEVIATIONS

PDs include deviations from inclusion and/or exclusion criteria and deviations from the protocol during the conduct of the study, classified as per latest version of PD code list. Each PD is reported in the SDTM DV domain and categorized according to time period:

1. PD at Screening
2. PD during Run-in period
3. PD at Visit 4 / Pre-randomization

4. PD during DB treatment period
5. PD during withdrawal period and follow-up

Each PD is classified as important or not. Only important PDs during time periods 3, 4 and 5 will be summarized by treatment group for the RND set. (All PDs will be listed.)

Note that an important PD does not necessarily lead to exclusion from the PPS [see Section 7.1.6], whereas an unimportant PD may lead to exclusion from the PPS. The subset of PDs *leading to exclusion* from the PPS are:

1. Double-blind treatment duration less than 49 days: PV_PP.535.
2. No or no valid Week 8 SiDBP (hence, no primary endpoint): PV_PP.501 and PV_MM.501.
3. Anti-hypertensive treatment still ongoing at randomization: PV_MM.307.
4. Taking medication during the double-blind treatment interfering with the primary efficacy parameter (SiDBP): PV_MM.503, PV_MM.504, PV_MM.506, PV_MM.507, PV_MM.508, PV_MM.509, PV_MM.534.
5. Compliance with double-blind treatment < 80% or > 120% or treatment not taken as per protocol: PV_PP.502 and PV_MM.515.

Note that exclusion will be done on a subject basis (rather than on subject / visit basis). In this particular study this approach is not unreasonable since PDs 1–5 are related to the 8 week DB treatment period and the primary efficacy endpoint is measured at the end of that period.

The one PD *leading to exclusion* from the Pharmacokinetic (PK) Set [see Section 7.1.6] is that the PK sample for that subject/visit was not taken at trough: PV_MM.512.

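### No rule visible in the SAP limits the time since last intake for a PK or ET-1 trough, so a sample taken after missed doses could be summarised as a steady-state trough

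*SAP*

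**What the plan says.** SAP 5.9 describes the ET-1 measurements at Weeks 2, 4 and 8 as steady-state trough concentrations and then gives the working rule: "Trough is defined as a sample taken in the morning of the visit prior to study treatment administration of that visit". The schedule footnote in SAP 2.2, which covers PK and PD samples together, says "Sample to be taken at trough (i.e., prior to study treatment intake", and Protocol 7.4.1 also anchors trough only to the morning dose that follows. None of these places sets a minimum or maximum time since the dose before.

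Other relevant provisions:

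- **Interruptions (Protocol 5.1.10).** "If treatment is stopped for more than 4 consecutive days, re-introduction is not permitted and treatment must be permanently discontinued". Gaps of up to 4 days may therefore be followed by resumed dosing.
- **Compliance (SAP 5.3.1, 5.3.2, 6).** Compliance is assessed over the whole double-blind period, and interruptions are not subtracted from the duration. Exclusion from the PPS follows below 80% or above 120%, or if treatment was not taken as the protocol requires (PV_PP.502, PV_MM.515).
- **PK Set (SAP 6, 7.1.7).** The set consists of PPS subjects with at least one evaluable trough sample; evaluable is not defined. The one deviation that excludes from the set is that "the PK sample for that subject/visit was not taken at trough" (PV_MM.512).
- **Summaries (SAP 10.13, 10.14).** ET-1 is analysed on the PK Set. Drug and ET-1 concentrations are summarised by active treatment and visit.
- **Dose times (Protocol 7.4.1).** The eCRF holds the clock time of each sample "as well as the exact dates and time of the drug administration prior and after blood draw".

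**The concern.** A pre-dose sample is a steady-state trough only if the preceding doses were taken on schedule. Under the written rule, a subject who skipped the previous day's dose, or who interrupted for up to 4 days and restarted at the visit, gives a sample 48 to 120 h after the last intake that still qualifies. Overall compliance would not reveal it, and the written definition gives PV_MM.512 no evident basis for removing it.

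At stake are the descriptive summaries of steady-state drug and ET-1 concentration, which serve the objectives in SAP 3.3. Low off-schedule values would pull the arithmetic mean down and widen the SD and CV%. The doses 5 and 10 mg, and 25 and 50 mg, differ only two-fold, and Protocol 1.2.1 reports dose-proportional exposure. A modest gap could therefore make one subject look like a subject on the next lower dose.

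**Working it through.** **Inputs.** Half-life about 44 h, accumulation about 3-fold and steady state by Day 8 (Protocol 1.2.1); once-daily dosing; longest gap after which dosing may resume, 4 days (Protocol 5.1.10); 80% compliance limit and 49-day minimum duration (SAP 6).

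**Check of the half-life against the protocol's own figures.**

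- Accumulation = 1 / (1 − 2^(−24/44)) = 1 / (1 − 0.685) = 3.18, in line with about 3-fold.
- Fraction of steady state after 168 h = 1 − 2^(−168/44) = 93%; after 192 h, 95%. Both fit steady state by Day 8.

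Mono-exponential decline with a 44 h half-life is therefore a fair approximation.

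**Concentration relative to a 24 h trough** = 2^(−(t − 24)/44), where t is hours since last intake.

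| Missed doses | t (h) | Fraction left | Lower by |
|---|---|---|---|
| 1 | 48 | 0.685 | 31.5% |
| 2 | 72 | 0.469 | 53.1% |
| 3 | 96 | 0.322 | 67.8% |
| 4 | 120 | 0.220 | 78.0% |

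With an assumed half-life of 40 to 48 h, the deficit is 29-34% at 48 h and 75-81% at 120 h.

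**Dose equivalents at 44 h.** A 10 mg sample after two missed doses corresponds to 10 × 0.469 = 4.7 mg, just below a normal 5 mg trough. A 50 mg sample after four missed doses corresponds to 50 × 0.220 = 11 mg.

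**Does compliance catch a 4-day gap?** From Day 1 to Day 55, 51/55 = 92.7%. At the 49-day minimum, 45/49 = 91.8%. Both lie well inside 80-120%.

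**Effect on an arm mean** = share affected × deficit. The share is not in the documents; 5% and 10% are assumptions.

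- 5% affected: 0.05 × 31.5% = 1.6%, up to 0.05 × 78.0% = 3.9%.
- 10% affected: 0.10 × 31.5% = 3.1%, up to 0.10 × 78.0% = 7.8%.

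**Effect of a window.** For intake 20 to 28 h before the draw, concentration differs from the 24 h value by only +6.5% to −6.1%.

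No comparable calculation is possible for ET-1, because the documents give no time course for its decline.

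**The case against.** Several points on the other side have force.

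*The SAP does not depart from the protocol.* A reader might infer a contradiction, because Protocol 6.1.1 speaks of "mean trough (i.e., 24 h post-dose) SiDBP, measured by OBPM". That wording concerns blood pressure. For PK and PD samples both documents consistently mean pre-dose, and Protocol 7.2.1 itself explains trough for blood pressure as before drug intake. The point is a refinement of a consistent rule.

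*Off-schedule samples may already be removed.* PV_MM.515 might catch skipped doses, PV_MM.512 might be operated using the recorded dose times, and evaluable might carry a time condition. The code list is not in the documents, the PK wording in SAP 5.10 is partly redacted, and the explicit definition stands in the ET-1 section. So one cannot say that no rule exists, only that none is visible. Interruptions that the protocol permits are the least clearly covered by PV_MM.515.

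*No affected sample is documented.* A reader might infer that samples 31-78% too low do enter the summaries. The documents show only that they could. The 78% case needs a four-day gap that ends on one of three visit days, with dosing resumed at that visit.

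*The consequences are limited.* These are objectives in the other category, the summaries are descriptive, and medians, ranges and listings would expose isolated low values. Including ordinary adherence is a defensible choice when describing exposure in the target population. Drug and ET-1 come from the same draw, so their correlation need not be biased.

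All of this lowers the weight of the point. None of it supplies the missing time condition, and a summary labelled steady state should have one.

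**Conclusion.** The point holds as a minor, inexpensive improvement. The visible rules set no limit on time since last intake, so samples 48 to 120 h after the last dose could be counted as steady-state troughs. Drug concentration in them would be about 31% to 78% below a 24 h trough, assuming mono-exponential decline at the 44 h half-life. The shift in arm means is roughly 1.6-8% if 5-10% of samples are affected, and smaller if they are rarer; the true share is unknown. The ET-1 effect cannot be quantified. Neither a conflict between SAP and protocol nor actual contamination of the summaries is shown. The primary SiDBP analysis does not depend on this definition.

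**What to change.** In SAP 5.9, 5.10, 6 (PV_MM.512) and 7.1.7, define an evaluable steady-state trough as a pre-dose sample whose recorded last intake was on the previous day, for example 20-28 h before the draw. Apply this per subject and visit, as SAP 6 already words the PK exclusion, to the by-visit PK and ET-1 summaries. Keep the excluded samples, flagged, in the listings.

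The cost is a few sentences and one derived variable from dose and sample times already in the eCRF. The drawback is slightly fewer samples per visit.
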